7.1.2 Analysis Methods for the Primary Efficacy Outcome Measure

Progression-free survival in the Part 2 treatment groups will be compared with a 1-sided log-rank test. The log-rank will be the primary assessment. Kaplan-Meier (KM) median PFS times and their 95% confidence intervals, estimates of first and third quartiles, as well as KM curves will be summarized by treatment group. A Cox regression model will be used to compare the hazard rate between the two treatment groups without stratification. A single hazard ratio and its 95% confidence interval will be calculated.

Results of tumor scans and related response assessments for subjects enrolled in this study will be included in by-subject data listings.

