2.3 Sample Size and Power Calculations

The final sample size of Part 1 (Safety Run-in) is dependent on the pre-stated rules for dose escalation. In Part 1, the sample size for each dosing regimen (ie, imalumab + 5-FU/LV and imalumab + panitumumab) is expected to be between 6 and 12 subjects (ie, 3 to 6 subjects at each 7.5 mg/kg and 10 mg/kg imalumab dose level). Non-evaluable subjects will be replaced to meet study objectives.

The sample size of Part 2 (Exploratory Phase 2a) is estimated to be a total of 66 subjects. Assuming that the median PFS is 2.4 months in the control arm and 4.25 months in the experimental arm (a constant hazard ratio 0.565), and using a one-sided log-rank test with α of 0.15 and β of 0.20 with a drop-out rate of 20% at 6 months, 48 PFS events are needed. With an enrollment ratio of 2:1, and taking into account the time for accrual of 1 year and an additional follow-up period of 6 months after the last subject is enrolled, the sample size needed is approximately 22 subjects in each of the 2 imalumab-containing treatment arms (imalumab + panitumumab and imalumab + 5-FU/LV) and in the control arm (SoC).

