2.4 Randomization

There is no randomization in Part 1. In Part 2, randomization in permuted blocks will occur to minimize bias and fulfill a 2:1 ratio between Arm A and Arm B. Prior to randomization, subjects will be stratified according to their KRAS and NRAS mutation status. Randomization will occur via an IRT System until the targeted number of subjects in each treatment-arm is achieved.

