7.2 Analysis of Secondary Efficacy Outcome Measure

7.2.1 Derivation of Secondary Outcome Measures

7.2.1.1 Overall Survival

Overall survival is defined as the time from randomization until death due to any cause. Any subject not known to have died at the time of analysis will be censored based on the last recorded date on which the subject was known to be alive.

Last date known to be alive will be obtained from the survival follow-up CRF. If that CRF hasn't been completed the following CRF fields will be used to determine the last date known to be alive:

- Dates of administration of chemotherapy and study drug
- Laboratory specimen collections dates
- PK/PD blood sampling dates
- CT and/or MRI scan dates
- Date of vital sign assessments
- Date of ECG assessments
- Date of contact on the survival follow-up CRF
- Date of Quality of Life assessments
- Start and stop dates for concomitant treatments
- Date of onset and resolution of AEs
- Completion/termination date.

Overall survival will be analyzed with the methods used for the analysis of PFS.

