7.2.1.2 Overall Response Rate

Tumor response will be assessed by the investigator based on the revised RECIST guidelines (Version 1.1) at each radiographic assessment. Radiological exams are required every 8 weeks (± 7 days) starting from date of randomization without delays for toxicity until protocol-defined disease progression is noted. Results based upon scans performed after start of new anti-cancer therapy will be excluded when calculating the best overall response. Objective response rate will be defined as the proportion of subjects with a complete response (CR) or a partial response (PR) per RECIST based upon the best response as assessed by the investigator; confirmation of response is not required. Clinical benefit rate (CBR) will be defined as the proportion of subjects with a complete response (CR), a partial response (PR), or stable disease (SD) per RECIST based upon the best response as assessed by the investigator. The analysis of ORR and CBR will be performed using Fisher's exact test to compare the relative rate of subjects with an objective response in the treatment groups without stratification. Clopper-Pearson exact 2-sided 95% confidence limits will be calculated for the proportion of subjects with ORR in each arm.

Since the presence of measurable disease is an inclusion criterion, the denominator for the rate will be the number of subjects in the FAS. In addition to representing ORR and CBR, the best overall response (BOR) using response categories CR, PR, SD, progressive disease (PD), and not evaluable (NE) will be tabulated. The proportion of subjects in each response category will be calculated for the study cohorts and the integrated treatment groups.

Subjects who do not have any post-baseline tumor assessment will be counted under the category Not Evaluable (NE).

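### Part 2 is randomised within KRAS/NRAS strata, but no planned efficacy comparison uses them; if the strata differ materially in prognosis, the PFS test loses power and the hazard ratio moves toward 1

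*SAP*

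**What the plan says.** SAP 2.4 makes RAS status a randomisation factor: "Prior to randomization, subjects will be stratified according to their KRAS and NRAS mutation status". SAP 2 and Protocol 8.2.2 fix the 2:1 ratio within each stratum.

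The efficacy analyses then leave the factor out:

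- **PFS, primary test.** SAP 7.1.2 and Protocol 13.4.3.2 name a one-sided log-rank test and do not mention strata.
- **PFS, hazard ratio.** SAP 7.1.2: "A Cox regression model will be used to compare the hazard rate between the two treatment groups without stratification".
- **OS.** SAP 7.2.1.1: "Overall survival will be analyzed with the methods used for the analysis of PFS".
- **ORR and CBR.** SAP 7.2.1.2 uses Fisher's exact test "to compare the relative rate of subjects with an objective response in the treatment groups without stratification".
- **PFS sensitivity analyses.** SAP 7.3 reuses the same log-rank test and Cox model.

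SAP 5.5, which lists changes from the protocol, says nothing about stratification. The strata appear only in descriptive output: median PFS per stratum (Protocol 13.4.3.2), ORR and CBR by KRAS status (Protocol 13.4.4.3), and treatment groups split by mutation status (SAP 5.4, Table 1).

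**The concern.** The usual practice is to analyse by the factor that restricted the randomisation. When that factor predicts outcome, an analysis that ignores it is conservative, and its hazard ratio is pulled toward 1.

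The documents give reason to expect that the strata differ. Arm A receives panitumumab in one stratum and 5-FU/LV in the other. Arm B may receive panitumumab only if the tumour is wild type (Protocol 8.2.2 and 8.7.4.2.2). Protocol 6.1.5.4 says that the patients who benefit from panitumumab are those with all-RAS wild-type tumours.

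The sample size assumes one constant hazard ratio and no difference between strata, with about 80% power at 48 events and no margin. The handling of strata in the primary test is also unwritten. In an open-label trial that leaves two candidate primary p-values.

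**Working it through.** **Inputs from SAP 2.3 and Protocol 13.1.** Median PFS 2.4 against 4.25 months, hazard ratio 0.565; "using a one-sided log-rank test with α of 0.15 and β of 0.20"; 2:1 allocation; 66 subjects (44 and 22); "48 PFS events are needed"; 12 months of accrual plus 6 of follow-up; "with a drop-out rate of 20% at 6 months".

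**Reproducing the plan's figures.** Schoenfeld's formula with allocation 2/3 : 1/3:

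- Events = (1.036 + 0.842)² / [(2/3)(1/3)(ln 0.565)²] = 3.527 / 0.0724 = 48.7, against 48 stated.
- Power at 48 events = Φ(√(48 × 2/9) × 0.571 − 1.036) = Φ(0.828) = 79.6%.
- With exponential PFS and drop-out, the average event probability is 0.766. Then 48.7 / 0.766 = 63.6, so 64, which becomes 66 for a 2:1 split.

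The plan's numbers hold for a population with no difference between strata.

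**Adding a prognostic difference.** The documents give no hazard ratio between strata, so 1 to 4 was assumed. Simulation: 66 subjects, 2:1 within two strata, exponential times, overall control median 2.4 months, treatment hazard ratio 0.565 in both strata, data cut at the 48th event. The base case has equal strata, because SAP 2.3 expects about 22 subjects per imalumab combination. Power uses 6,000 trials per scenario, so the Monte Carlo standard error is √(0.8 × 0.2 / 6000) = 0.5 points.

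| Prognostic ratio | Power, unstratified | Power, stratified | Difference (points) | Cox HR, unstratified | Cox HR, stratified |
|---|---|---|---|---|---|
| 1 | 80.8% | 79.6% | +1.2 | 0.555 | 0.556 |
| 1.25 | 80.5% | 79.7% | +0.8 | 0.562 | 0.560 |
| 1.5 | 78.8% | 79.1% | −0.3 | 0.570 | 0.562 |
| 2 | 77.6% | 79.6% | −2.0 | 0.580 | 0.559 |
| 3 | 73.2% | 79.3% | −6.1 | 0.616 | 0.562 |
| 4 | 69.6% | 79.7% | −10.1 | 0.633 | 0.554 |

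With strata of 67:33, the poorer-prognosis stratum being the larger (4,000 trials each), the loss is smaller:

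- 1.5-fold: 80.5% unstratified against 79.9% stratified.
- 2-fold: 78.3% against 78.1%, unstratified HR 0.574.
- 3-fold: 76.0% against 78.8%, unstratified HR 0.591.

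A separate simulation with equal strata gave 77% against 78% at 2-fold, 73% against 80% at 3-fold and 69% against 79% at 4-fold.

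To put the 3-fold row in events: by the same formula, 73.2% power needs (1.036 + 0.619)² / 0.0724 = 37.8 events and 79.3% needs 47.4. The loss is worth about 10 events.

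**Test size with no treatment effect, nominal 0.15.** In the same simulation at ratios 1, 2 and 3, the unstratified test rejects 0.158, 0.152 and 0.145, and the stratified test 0.154, 0.157 and 0.165. A second set of 4,000 null trials per scenario, at ratios 1 to 4, gave 0.156, 0.157, 0.140 and 0.125 unstratified, and 0.156, 0.164, 0.162 and 0.166 stratified.

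Part of the power gap is therefore a difference in size. A rough adjustment moves the unstratified test to the stratified test's size:

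- 3-fold: Φ(Φ⁻¹(0.732) + 1.058 − 0.974) = 75.9%, which closes 2.7 of the 6.1 points.
- 4-fold: Φ(Φ⁻¹(0.696) + 1.150 − 0.970) = 75.6%, which closes 6.0 of the 10.1 points.

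**Relaxing the common hazard ratio.** With assumed ratios of 0.4 in the better-prognosis stratum and 0.8 in the other (equal strata), the unstratified test is stronger: 78.7% against 73.3% at 1.5-fold, 77.7% against 72.5% at 2-fold, and 73.9% against 70.6% at 3-fold. With the two reversed, stratifying loses slightly at 1.5-fold (79.6% unstratified, 78.2% stratified) and gains at 2-fold (77.7%, 79.7%) and 3-fold (73.9%, 81.4%).

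**The case against.** The strongest reply is that an unstratified log-rank test after stratified randomisation is valid, Part 2 is labelled exploratory, and material loss needs a 3- to 4-fold prognostic gap for which the documents offer no figure. All of that stands. So does the point that different partner drugs make unequal treatment effects plausible. In that case the direction of the power difference is not settled.

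It can also be said that if 0.565 is the overall hazard ratio, averaged over strata, the unstratified test has its planned 79.6%. That is correct for a constant overall ratio, and stratifying would then only add power. However, with exponential times and a common within-stratum ratio, the ratio of the arm medians equals that within-stratum ratio whatever the gap: 2.4 / 4.25 = 0.565. Runs that fixed the two medians instead showed much the same loss (78.1% against 80.2% at 2-fold, 74.2% against 79.9% at 3-fold).

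Four stronger readings are tempting but not supported:

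- A reader might infer that power falls below 80% whenever the strata differ. Up to about 1.5-fold, the two tests cannot be told apart in any way that matters.
- A reader might infer that the primary log-rank test is declared unstratified. Those words are attached only to the Cox model and Fisher's test. For the log-rank test it is the default reading of a silent text.
- A reader might attach the stated 80% to OS or response. SAP 2.3 states power for PFS only.
- A reader might suspect extra false positives. Ignoring the strata does not cause them.

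**Conclusion.** The point holds as a mismatch between design and analysis, with a conditional cost. No efficacy comparison uses the randomisation strata, and the primary test does not say how they are handled.

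The size of the cost rests on two assumptions that the documents do not supply: the prognostic ratio between strata, and a common treatment hazard ratio of 0.565. Under them, the loss of PFS power is negligible to about 1.5-fold, 0 to 3 points at 2-fold, about 3 to 7 at 3-fold depending on the stratum split, and about 10 at 4-fold with equal strata. The attenuation of the hazard ratio follows the same gradient. Some of the 3- to 4-fold gap reflects the unstratified test being conservative there and the stratified test running slightly above nominal.

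For OS, ORR and CBR no power is stated and none was computed, so there the finding is the mismatch alone.

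**What to change.** In SAP 7.1.2, specify the primary one-sided log-rank test and the Cox model as stratified by the KRAS/NRAS stratum used at randomisation, and keep the unstratified versions as sensitivity analyses in SAP 7.3. Define the stratum as the one recorded at randomisation, since Protocol 11.3 allows treatment to start while the NRAS result is pending. Apply the same to OS, and replace Fisher's test for ORR and CBR by an exact stratified test of Cochran-Mantel-Haenszel type. Record the change in SAP 5.5.

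Date it before outcome data by arm are analysed. SAP 5.5 explains the dropped interim analysis by the short interval between 33 and 48 events, so little time may remain. If it is too late, add the stratified versions as labelled sensitivity analyses and give the reason for the unstratified primary.

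The cost is SAP wording and one stratification statement per model. The statistical downside is about 1 point of power if the strata turn out equal (79.6% against 80.8%), and a simulated size of about 0.154 to 0.166 for the asymptotic stratified test against nominal 0.15. The SAP should acknowledge both.

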7.2 Analysis of Secondary Efficacy Outcome Measure

7.2.1 Derivation of Secondary Outcome Measures

7.2.1.1 Overall Survival

Overall survival is defined as the time from randomization until death due to any cause. Any subject not known to have died at the time of analysis will be censored based on the last recorded date on which the subject was known to be alive.

Last date known to be alive will be obtained from the survival follow-up CRF. If that CRF hasn't been completed the following CRF fields will be used to determine the last date known to be alive:

- Dates of administration of chemotherapy and study drug
- Laboratory specimen collections dates
- PK/PD blood sampling dates
- CT and/or MRI scan dates
- Date of vital sign assessments
- Date of ECG assessments
- Date of contact on the survival follow-up CRF
- Date of Quality of Life assessments
- Start and stop dates for concomitant treatments
- Date of onset and resolution of AEs
- Completion/termination date.

Overall survival will be analyzed with the methods used for the analysis of PFS.

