10.5 Subject Completion/Discontinuation

A subject is considered to have completed the study when he/she ceases active participation in the study because the subject has, or is presumed to have, completed all study procedures according with the protocol (with or without protocol deviations).

Reasons for completion or discontinuation will be reported on the Completion/Discontinuation CRF, including: completed, screen failure, AE (eg, death), discontinuation by subject (eg, lost to follow-up [defined as 3 documented unsuccessful attempts to contact the subject], dropout), physician decision (eg, pregnancy, progressive disease, non-compliance with IP/protocol violation(s), recovery), study terminated by sponsor, or other (reason to be specified by the investigator, eg, technical problems). Regardless of the reason, all data available for the subject up to the time of completion/discontinuation should be recorded on the appropriate CRF.

Every effort will be made to have discontinued subjects complete the study completion/termination visit. If the completion/termination visit is done as an additional, unscheduled visit, the assessment results shall be recorded with the completion/termination visit. If a subject terminates participation in the study and does not return for the completion/termination visit, their last recorded assessments shall remain recorded with their last visit. The reason for discontinuation will be recorded, and the data collected up to the time of discontinuation will be used in the analysis and included in the clinical study report. If additional assessments are required, the assessments shall be recorded separately. Assessments to be performed at the termination visit (including in cases of withdraw or discontinuation) can be found in Section 20.2 Schedule of Study Procedures and Assessments.

In the event of subject discontinuation due to an AE, clinical and/or laboratory investigations that are beyond the scope of the required study observations/assessments may be performed as part of the evaluation of the event. These investigations will take place under the direction of the investigator in consultation with the sponsor, and the details of the outcome may be reported to the appropriate regulatory authorities by the sponsor.

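### The OS fallback rule accepts the completion/termination date as evidence of life, with no exception for loss to follow-up; OS is biased upward if that date falls after the last real contact

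*SAP*

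**What the plan says.** SAP 7.2.1.1 states the principle first: a subject not known to have died is "censored based on the last recorded date on which the subject was known to be alive". It then names the source: "Last date known to be alive will be obtained from the survival follow-up CRF". Only when that form has not been completed does a fallback list of eleven CRF items apply: "the following CRF fields will be used to determine the last date known to be alive". Most of them record something done with the subject (dosing, samples, scans, vital signs, ECG, questionnaires). The list also contains "Start and stop dates for concomitant treatments", the onset and resolution dates of adverse events and, as its last entry, "Completion/termination date". No condition is attached to any entry.

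Protocol 10.5 lists the reasons to be reported on the Completion/Discontinuation CRF, among them "lost to follow-up [defined as 3 documented unsuccessful attempts to contact the subject". It also foresees a subject who stops without attending the termination visit and says that "their last recorded assessments shall remain recorded with their last visit". It does not say which date is then entered as the completion or termination date.

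For PFS, SAP 7.1.1 (Table 2) censors withdrawn or lost subjects at the last scan before the withdrawal or loss. The sensitivity analyses in SAP 7.3 concern PFS only.

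**The concern.** A censoring date for OS should be a date on which someone had evidence that the subject was alive. For a subject lost to follow-up, a completion/termination date may mark an attended visit, but it may also mark the last failed attempt or the day the form was closed. In the latter two cases it is not evidence of life. The interval between the last real contact and that date would count as time alive, although a death in it would go unrecorded unless it came to light by another route.

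The result would be an upward bias in the Kaplan-Meier curve and median for OS. If losses differed between the arms of this open-label trial, the OS hazard ratio would also move, in favour of the arm that loses more subjects. Adverse-event resolution dates and concomitant-treatment stop dates raise the same question to a lesser degree, because they can be entered without a contact on that day.

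**Working it through.** **The plan's own figures.** The documents give no OS assumption, event target or power, so there is no OS figure to reproduce. The only powered figure is 48 PFS events (SAP 2.3). With one-sided α 0.15, power 0.80, HR 0.565 and 2:1 allocation, the Schoenfeld formula gives (1.036 + 0.842)² / [(2/3)(1/3)(ln 0.565)²] = 48.7. This agrees with the plan and is not affected by the present point.

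**When the date matters.** All of these must hold for a given subject:
1. The survival follow-up CRF has not been completed.
2. The completion/termination date is later than the last real contact.
3. It is also later than every other listed date.

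The documents settle none of these for a lost subject.

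**Direction.** If lost subjects are carried forward by a lag g, the number of recorded deaths is unchanged while time at risk increases. With loss rate μ per month, each month at risk yields μ losses, and each loss adds g months. Hence

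estimated death rate / true death rate ≈ 1 / (1 + μg), with μ = −ln(1 − p)/6 for a proportion p lost at 6 months.

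- p = 5%: μ = 0.0085, ratio 0.992 (g = 1 month) or 0.975 (g = 3)
- p = 20%: μ = 0.0372, ratio 0.964 (g = 1) or 0.900 (g = 3)

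**Size, by simulation.** All inputs are assumptions except the follow-up range. OS is exponential with median 6 or 9 months. Administrative censoring is uniform over 6–18 months (1 year accrual plus 6 months, SAP 2.3). Every lost subject goes through the fallback, and the lag is cut at the administrative date. Each row compares censoring at last contact plus lag with censoring at last contact.

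| Loss at 6 months | Lag (months) | Death-rate ratio | Rise in KM median OS |
|---|---|---|---|
| 5% | 1 | 0.992 | 0.8–0.9% |
| 5% | 3 | 0.977 | 2.2–2.4% |
| 10% | 1 | 0.983 | 1.7–1.8% |
| 10% | 3 | 0.953–0.954 | 4.8–5.1% |
| 20% | 1 | 0.965 | 3.7% |
| 20% | 3 | 0.905–0.907 | 10.4–11.0% |

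The last row is a rise from 6.02 to 6.64 months, or from 8.99 to 9.98 months. The simulation agrees with the formula; the effect is slightly smaller at the longer lag because the lag is cut at the administrative date.

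**Between arms.** The ratio of estimated death rates stands in for the hazard ratio.
- Equal loss: the factor 1/(1 + μg) is the same in both arms and cancels.
- 5% versus 20% loss, no true effect, median 6 months: 1.028 (1-month lag) or 1.079 (3-month lag). With the arms reversed: 0.973 or 0.927.

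**Against sampling error.** Assume 33 to 50 OS deaths, roughly half to three quarters of 66. The standard error of the log hazard ratio is then √(4.5/d), which is 0.37 to 0.30. A shift of 0.03 to 0.08 on the log scale is about 0.1 to 0.25 of a standard error.

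**The case against.** A reader might infer that, as the plan is written, survival is overstated in the subjects lost to follow-up. The documents do not support that stronger statement, for these reasons:

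- **The governing sentence is sound.** It asks for a date the subject was known to be alive, and a date of failed contact does not meet it.
- **The list is only a fallback.** A missing survival form is not peculiar to lost subjects. Survival calls start after treatment stops or progression is documented (Protocol 10.3.3.10), and the analysis is run while the study continues (SAP 1). Subjects still on treatment would also have no form, and for them the fallback gives recent, valid dates.
- **The termination date often marks an attended visit.** Subjects who progress or stop early are asked to an End of Study/Early Termination visit (Protocol 10.3.3.8), and the survival calls come after it. A date set after failed attempts mainly concerns subjects lost before that visit, while visits are weekly. Nothing in the documents supports a lag of several months there.
- **The 20% drop-out is a PFS planning value.** Vital status is followed by telephone, so loss for OS may be smaller.
- **Stop dates cannot be called planned dates.** Protocol 12.5 records medications actually taken.

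These points limit the size and the certainty. They do not remove the defect: the SAP says that the listed fields will be used, puts no condition on the completion/termination date, and leaves undefined what that date means for a lost subject. A programmer who takes the latest listed date would follow the text and could still breach the principle. The survival form's own contact date also appears in the list used when that form is missing. That is redundant but produces no wrong date.

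**Conclusion.** The point holds as a conditional weakness in a stated derivation rule, not as a demonstrated bias. If the date entered for lost subjects is later than the last contact and than every other listed date, Kaplan-Meier OS is biased upward, and no other rule or OS sensitivity analysis would show it. The percentages in the working rest on assumed OS medians, loss rates and lags, and on sending every lost subject through the fallback. They are therefore an illustration towards the upper end, not an estimate for this trial. An effect on the hazard ratio needs unequal loss and is small beside the sampling error. SAP 5 treats secondary endpoints as supportive and their p-values as descriptive, and the primary PFS analysis does not use this rule. The correction is still worth making because it is cheap and aligns the list with its own principle.

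**What to change.** Amend SAP 7.2.1.1 as follows:

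- Use the completion/termination date only when the subject was seen or contacted alive on that date.
- When the reason for discontinuation is loss to follow-up, censor OS at the latest date, on or before the data cut-off, with documented direct contact: visit, dose, sample, scan, vital signs, ECG, completed questionnaire or answered survival call.
- Count concomitant-treatment and adverse-event dates only when they were confirmed at a contact.
- Report the number of subjects lost to follow-up by arm, so that the reader can judge any imbalance.

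The cost is a short text change and one derivation. The downside is slightly earlier censoring, and so a little less nominal follow-up, for a few subjects.
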